4.3.4 Activity

Subjects will be instructed to refrain from abnormal strenuous physical activity which could cause muscle aches or injury, including contact sports at any time from 48 hours prior to Screening and Check-in, and during confinement.

4.3.5 Tobacco Use/Considerations

Except as allowed by the study, consumption of tobacco- or nicotine-containing products will not be permitted from Check-in through discharge. On Days -1 through 4, subjects will be allowed to use their OBCCs, *ad libitum*, after completion of study assessments and after the 4-hour *ad libitum* product use session, but will abstain from use of any tobacco- or nicotine-containing products for at least 12 hours prior to the start of morning controlled product use session scheduled on the following day.

4.4 Subject Early Discontinuation or Withdrawal

Subjects will be advised that they are free to withdraw from the study at any time. In addition, subject participation in this study may be discontinued for any of the following reasons:

- AE
- Lost to follow-up
- Non-compliance with study procedures
- Protocol violation
- Study terminated by Sponsor or other regulatory authorities
- Withdrawal of consent
- Investigator's discretion, including a severe laboratory abnormality or other medical condition that indicates to the Investigator that continued participation is not in the best interest of the subject

Protocol deviations/violations should not lead to subject withdrawal unless they indicate a significant risk to the subject's safety or jeopardise the scientific integrity of the study.

If premature withdrawal from the study occurs for any reason, the Investigator must determine the primary reason and record this information in the case report form (CRF). Additionally, subjects withdrawing after study product administration will undergo all discharge safety procedures as feasible and as deemed necessary by the Investigator.

A subject withdrawn from the study due to any AE or clinically significant abnormal laboratory test values will be evaluated by the Investigator or other qualified individual and will be treated and/or followed up until the symptoms or values return to normal or acceptable levels or until lost to follow-up, as appropriate in the opinion of the Investigator.

Subjects withdrawing or removed from this study cannot re-enter.

4.5 Subject Randomisation

Subjects who complete the study screening assessments and meet all the eligibility criteria and are randomised will be assigned a unique randomisation identification number on Day 1 and will receive study products according to the randomisation scheme generated by Celerion.

The sequences to be used in the randomisation will be ABCD, BDAC, CADB, and DCBA.

If replacement subjects are used, the replacement subject number will be 100 more than the original (e.g., Subject No. 101 will replace Subject No. 1).

5. STUDY PRODUCTS/MATERIALS

5.1 Description of Study Products

All subjects will use Products A through D.

The following study products will be used in this study:

Product Designation	Study Product Name
A	████████ HT device with ██████████ stick
B	████████ HT device with ██████████ stick
C	████████ HT device with ██████████ stick
D	Subject's own brand combustible cigarette (OBCC)

5.1.1 Usual Brand Combustible Cigarette

Subjects will be required to bring with them to the CRU a sufficient supply (i.e., 5-day supply [unopened packs]) of their OBCCs for personal use throughout confinement.

5.1.2 [REDACTED] HT Device with Stick

[REDACTED] works by the user inserting a specially designed consumable ([REDACTED]) into the handheld device which contains an electronically controlled heater ([Figure 2](#)). The handheld device heats the tobacco using an electronically controlled heating rod. The rod can be set to 2 temperatures: Eco mode (315°C) or Standard mode (345°C). The handheld device supplies heat to the tobacco using the heating rod for 4 minutes. The heating device must be recharged after 20 consecutive uses.

The inclusion of a foil wrap around the tobacco portion of the rod prevents the [REDACTED] stick from being lit and combusted like a CC ([Figure 3](#)).

Figure 2. Heated Tobacco Product Diagram

[figure not shown]
A

B

Figure 1A. [REDACTED] device features; Figure 1B. Assembly of the [REDACTED] device

Figure 3. ■ Stick Assembly

5.2 Study Product Accountability and Dispensing

All ■ HT Devices and tobacco ■ sticks will be provided by the Sponsor. The CRU staff will coordinate shipping of products and devices from the Sponsor. The staff will document the date each shipment was received and recorded in the inventory records. The CRU staff will document and reconcile the total number of products shipped to the CRU, the total number of products dispensed during the study, and the total number of products remaining at the end of clinical conduct. Subjects will bring a 5-day supply (unopened packs) of their OBCCs for personal use at designated times throughout confinement in the CRU.

For each day of HT product use, subjects will be provided with a new/unused device to be used for the morning controlled product use and *ad libitum* product use sessions. A fresh tobacco stick will be provided at the start of the morning controlled product use session and at the start of puff topography.

All products will be stored in a locked, limited-access area at the CRU and kept at controlled room temperature (defined as 20 - 25°C [68 - 77°F], with excursions permitted to 15 - 30°C [59 - 86°F]). Humidity is recorded but not controlled.

Study products for dispensing (including OBCC) to subjects will be prepared by the study staff according to instructions provided by the Sponsor. Individual study product dispensing records will be maintained by the CRU staff for each subject. Care should be taken when repackaging the study products for use at the CRU to avoid exposure to air and moisture to the extent possible. The pharmacy will maintain records of the number of cigarettes dispensed for each subject.

The study staff will document the start time and stop time of each product use session. The number of HT sticks used and cigarettes smoked will be documented during each *ad libitum* product use session on Days 1 through 4. The number of cigarettes smoked will be

documented on Day -1 prior to smoking abstinence (at least 12 hours prior to the start of morning controlled product use session on Day 1), and on Days 1 through 3 following the 4-hour *ad libitum* product use session until at least 12 hours prior to the start of morning controlled product use session scheduled on the following day.

Subjects will smoke their OBCC and use each assigned product only in designated areas of the CRU.

Opened and unopened packages of [REDACTED] HT devices and sticks will be returned to the Sponsor or destroyed at the direction of the Sponsor. Opened and unopened packages of subject's OBCC will be returned to the subjects at the end of the study. All returns or destruction of study products will be documented.

[REDACTED] HT device has two power settings: standard mode (345°C temperature) and Eco (315°C temperature). **Subjects should use the device set on the standard mode.**

6. STUDY PROCEDURES

6.1 Screening

Potential subjects will undergo Screening procedures to ensure that they meet the requirements for inclusion in the study within 27 days prior to study procedures on Day -1.

Screening procedures will be performed as delineated in the Study Events Flow Chart ([Table 1](#)).

6.1.1 Informed Consent

All prospective subjects will have the study explained by the Investigator or his/her designee and will be required to read, sign, and date an ethics committee (EC)-approved ICF prior to completion of screening or other study procedures. This consent form will provide the subjects in non-technical terms with the purpose of the study, procedures to be carried out, and potential hazards. The subjects will be assured that they may withdraw from the study at any time without jeopardising medical care related to or required as a result of study participation. Subjects will be given a copy of their signed ICF.

6.1.2 Medical History/Demographic Data/Record of Concomitant Medication

Medical history and socio-demographic data, including name, sex, age (each subject must show proof of age with government-issued identification [e.g., driver's license]), race, ethnicity, address, and phone number will be recorded at Screening for each subject.

Additional data including National Insurance Number, as applicable, will be recorded at Check-in.

Any concomitant medications taken from 30 days prior to Check-in through discharge will be recorded in the CRF and source document.

6.1.3 Tobacco/Nicotine Product Use History

Subjects will be required to report previous tobacco-product and nicotine-product use histories to satisfy the study inclusion and exclusion criteria.

Details of the subject's OBCC, including the brand, brand style, flavour, cigarette length, and amount of daily use will be recorded at Screening and updated at Check-in as necessary. A color photocopy or photograph of the subject's OBCC package (including the branding and the UPC code) will be taken by the CRU staff at Check-in.

6.1.4 Exhaled Carbon Monoxide

Exhaled CO levels will be measured using a Bedfont Micro+ Smokerlyzer or similar device, at Screening and at Check-in.

6.2 Check-in and Confinement

Subjects will check in to the CRU on Day -1 at a time specified by the CRU. Check-in procedures will be performed as delineated in the Study Events Flow Chart ([Table 1](#)).

After check-in, subjects will complete one set of questionnaires for the purpose of familiarisation with subjective effects questions, appropriate use of the VAS, and use of the computerised tablet system. Data collected from the training session will not be used for any analysis.

The clinical team will explain how the HT products will be used. Subjects will have the opportunity to see the products/devices and packaging and will participate in a Product Trial where they will use the [REDACTED] device with the HT stick (flavour) of their choice. The HT stick flavour will be recorded; however, no assessments will be made. The purpose of the Product Trial is to familiarise subjects to the [REDACTED] device and HT stick prior to PK assessments. All products/devices used in the trial session will not be used in the clinical study but will be retained as demonstration samples for accountability purposes.

Subjects will have their personal belongings thoroughly checked during Check-in. All subjects will be required to shower and will receive clean articles of clothing prior to the start of each morning controlled product use (i.e., during the 12-hour abstinence) on Days 1, 2, 3 and 4.

Subjects will be confined from Check-in on Day -1 through completion of scheduled study events on Day 4.

A subject may be required to remain at the CRU for longer at the discretion of the Investigator or designee.

6.2.1 Baseline Assessments (Day -1)

Subjects will continue to smoke their OBCC from Check-in (after completion of the Product Trial and check-in procedures) through Day -1, but will abstain from use of any tobacco- or

nicotine-containing products for at least 12 hours prior to the start of morning controlled product use session on Day 1.

The number of OBCC smoked per day will be documented.

Baseline assessments will be performed as delineated in the Study Events Flow Chart ([Table 1](#)).

6.3 Product Use (Days 1 Through 4)

On Days 1, 2, 3, and 4, subjects will use the study product they are assigned to use according to the randomisation scheme.

In the morning of each day, subjects will use the assigned study product under controlled conditions (i.e., completely use a single unit of the assigned study product, with puffs taken at 30-second intervals and puffs 3 seconds in duration). Following the 4-hour PK blood collection, subjects will start a 4-hour *ad libitum* product use session (no limits on cigarette or HT consumption) with the same study product used during the morning controlled use session.

Each subject will be provided with a new/unused [REDACTED] HT device for each day of HT product use (i.e., the same device will be used for the morning controlled product use session and the *ad libitum* product use session on the same day). Subjects will be provided the assigned HT stick (based on randomisation sequence) or OBCC on each day. The clinic staff will document the time each product is dispensed. **The Pulze HT device should be used on the Standard Mode Setting.** Products that stop functioning should be replaced as soon as possible, with the failure documented.

6.4 Study Assessments

All study assessments will take place at the times delineated in the Study Events Flow Chart ([Table 1](#)) unless otherwise noted below.

Any nonscheduled procedures required for urgent evaluation of safety concerns take precedence over all routine scheduled procedures.

6.4.1 Nicotine Pharmacokinetics

On each of Days 1, 2, 3 and 4, a 4 mL blood sample for plasma nicotine analysis will be drawn into a plastic K₂-EDTA (lavender top) vacutainer tube at the time points delineated in the Study Events Flow Chart ([Table 1](#)). Allowable deviation windows for PK sampling are: \pm 30 seconds for samples collected from 3 - 15 minutes, \pm 1 minute for samples collected from 30 - 60 minutes, and \pm 3 minutes for all other samples.

PK blood samples will be collected by direct venipuncture or through an intravenous catheter port as determined by the clinical staff.

Additional blood (typically up to approximately 1 mL) may be drawn between blood draws for the purpose of keeping the needle patent, if required. The blood from the 1 mL draws will be discarded. In total, approximately 250 mL of blood will be drawn from each subject during the entire study for nicotine PK analysis.

The blood samples collected for plasma nicotine analysis may be kept at room temperature prior to centrifugation, and will be centrifuged at approximately 1000 to 1300 RCF at ~5°C for approximately 10 minutes, within 60 minutes from collection. After centrifugation, the plasma will be transferred to two methanol prewashed 3.5 mL polypropylene screw cap tubes, properly labeled, and then stored at -20°C (± 10°C) or below (within 120 minutes from collection) until analysis.

Samples will be analyzed using a validated liquid chromatography coupled to tandem mass spectrometry detection analytical method with the appropriate quality controls in accordance with FDA Good Laboratory Practice regulations (Title 21 Code of Federal Regulations [CFR] Part 58). Additionally, processing of samples will be completed by a non-tobacco user.

6.4.1.1 Future Research

No additional analysis is planned to be performed on the blood samples for possible future research.

6.4.2 Subjective Effects Questionnaires

The Intent to Use (VAS), Urge to Smoke (VAS), and Product Evaluation Scale (7-point scale) questionnaires will be completed using a computerised tablet device. All relevant software and staff training specific to the electronic questionnaires will be provided by IVRCC ePro. Any electronic device used must meet all regulatory requirements, including FDA 21 CFR Part 11.

All questionnaires will be completed at the time points delineated in the Study Events Flow Chart ([Table 1](#)).

When scheduled at the same time as a PK blood draw, the Urge to Smoke questionnaire will be completed approximately 30 seconds prior to the scheduled blood draw (except for the one scheduled at Time 0, which will be performed approximately 10 minutes prior to the start of the product use session), and all other questionnaires will be completed within approximately 2 minutes after the last scheduled blood draw.

6.4.3 Puff Topography

Puff topography will be evaluated over the last 2-hour period during the 4-hour *ad libitum* product use session on Days 3 and 4 as indicated in the Study Events Flow Chart ([Table 1](#)). Following the 4-hour PK blood collection and at the start of their meal, subjects will be allowed to use their assigned study product *ad libitum* for 4 hours. During the last 2 hours of the *ad libitum* session, topography measurements will be taken. The topography session will span a 2-hour period and the SPA-M topography device will be stopped and restarted with each new stick or cigarette during that time. Puff parameters will be recorded using SPA-M

devices (puff count, puff duration, puff volume, peak puff flow rate, average puff flow rate, inter puff interval) for each product.

The *ad libitum* product use session on Days 1 through 4 will start at approximately the same time each day, with lunch served at the start of the *ad libitum* product use session, at approximately the same time each day. After completion of the *ad libitum* use session (i.e., approximately 8 hours after the start of the morning controlled product use), subjects will be allowed to smoke their own cigarettes (*ad libitum*) but will abstain from use of any tobacco- or nicotine-containing products for at least 12 hours prior to the start of morning controlled product use session scheduled on the following day.

The topography device will be monitored to ensure the device is actively recording during each session.

Additional details and instructions for puff topography procedures will be provided separately.

Depending on the availability of topography equipment, puff topography may not be performed for some or all assigned subjects.

6.4.4 Safety Assessments

Safety assessments in addition to those below may be obtained as necessary at the discretion of the Investigator. In the case of an early subject withdrawal, discharge safety assessments should be collected to the extent possible.

6.4.4.1 Physical Examination

A standard physical examination assessing the general physical well-being will be performed at Screening. A symptom-driven physical examination will be conducted at other times as deemed appropriate by the Investigator ([Table 1](#)).

6.4.4.2 Body Weight, Height, and BMI

Body weight and body height will be measured as delineated in the Study Events Flow Chart ([Table 1](#)). BMI will be recorded as kg/m².

6.4.4.3 Electrocardiogram

Single 12-lead ECGs will be performed as outlined in the Study Events Flow Chart ([Table 1](#)). ECGs will be taken following resting in the supine position for at least 5 minutes. All ECG tracings will be reviewed by the Investigator or a qualified designee.

6.4.4.4 Vital Signs

Single measurements of vital signs (respiratory rate, HR, BP, and oral temperature) will be performed as outlined in the Study Events Flow Chart ([Table 1](#)). Additional vital signs may be taken at any other times, if deemed necessary.

BP and HR measurements will be taken following a rest period of at least 5 minutes in a seated position. Vital signs are to be measured at least 15 minutes after the last tobacco- or nicotine-containing product used.

On Days 1, 2, 3 and 4, vital signs measurements will be taken within 2 hours prior to the start of the morning product use session.

6.4.4.5 Clinical Laboratory

All clinical laboratory tests will be conducted by an accredited laboratory. Values for the clinical laboratory parameters are to be within the laboratory normal ranges or deemed not clinically significant in the opinion of the Investigator. All tests listed below will be performed as delineated in the Study Events Flow Chart ([Table 1](#)). Up to approximately 38 mL of blood will be drawn from each subject during the entire study for clinical laboratory tests.

Serum Chemistry¹

- Albumin
- Alkaline phosphatase
- Alanine aminotransferase
- Aspartate aminotransferase
- Bicarbonate
- Blood urea nitrogen
- Creatinine
- Glucose
- Potassium
- Sodium
- Total protein
- Uric acid

Urinalysis²

- Bilirubin
- Blood
- Glucose
- Ketones
- Leukocyte esterase
- Nitrite
- pH
- Protein
- Specific gravity
- Urobilinogen

Additional Tests

- Serology
 - HIV
 - HBsAg
 - HCV
- Serum pregnancy test³
- Serum FSH⁴
- Urine cotinine
- Urine drug screen
 - Amphetamines
 - Cannabinoids
 - Cocaine
 - Opiates
- Urine/breath alcohol

Hematology

- Hematocrit
- Hemoglobin
- Platelet count
- Red blood cell count
- White blood cell count with differential

¹ Serum chemistry tests will be performed after at least an 8-hour fast; however, in case of dropouts or rechecks, subjects may not have fasted for 8 hours prior to the serum chemistry sample being taken. For the samples collected at EOS, an 8-hour fast is not required.

² A microscopic examination for red blood cells, white blood cells, bacteria, and casts will be performed if an abnormality is noted in leukocyte esterase, protein, blood, or nitrite.

³ Human chorionic gonadotropin (females only).

⁴ For postmenopausal females only.

6.4.5 Adverse Events

An AE is any untoward medical occurrence associated with the use of the study product, whether or not considered study product-related. An AE can therefore be any unfavorable and unintended sign (including an abnormal laboratory finding), symptom, or disease temporally associated with the use of a study product, whether or not related to the study product.

6.4.5.1 Monitoring

The subjects will be instructed to inform the Investigator or staff of any AEs and intercurrent illnesses experienced during the study (i.e., from Screening until follow-up). Additionally, a specific inquiry regarding AEs will be conducted prior to each product use and at discharge (or upon early withdrawal). The inquiry will be posed in a non-specific manner using open-ended questions so as not to bias the response (e.g., How are you feeling today?).

A subject who has any clinically significant AE or clinically significant abnormal laboratory test value will be evaluated by the Investigator or other qualified individual and will be treated and/or followed up until the symptoms or values return to normal or acceptable levels (as appropriate in the opinion of the Investigator), or until the subject is lost to follow-up. Where appropriate, medical tests and examinations will be performed to document resolution of the event(s).

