On Day -1, following eligibility confirmation, subjects will undertake a familiarisation session of the study products and questionnaires. The clinical team will explain how the HT products will be used. Subjects will have the opportunity to see the products/devices and packaging and will participate in a Product Trial where they will consume one HT stick (flavour chosen by subject). All products/devices used in the trial session will not be used in the clinical study but will be retained as demonstration samples for accountability purposes. An explanation of how the questionnaires will be administered to the subjects will be given. After the familiarisation session and completion of check-in procedures, subjects will be allowed to smoke their own cigarettes *ad libitum* but will abstain from use of any tobacco- or nicotine-containing products for at least 12 hours prior to the start of the morning controlled product use session on Day 1.

In the morning of Day 1, after pre-use assessments and confirmation of eligibility, the subjects will be randomised to 1 of 4 product sequences and then provided a single product of the study product in the sequence to which they have been randomised. On Days 1 through 4, subjects will use the assigned study product under controlled conditions (i.e., completely use a single unit of the assigned study product, with puffs taken at 30-second intervals and puffs 3 seconds in duration). PK samples will be collected within 5 minutes pre-study product use and at 2, 4, 6, 8, 10, 15, 30, 45, 60, 120, and 240 minutes following the start of study product use. Questionnaires will be administered to the subject at defined intervals throughout the day. Safety will be monitored throughout the day.

On Days 1 through 4, following the 4-hour PK blood collection, subjects will start a 4-hour *ad libitum* product use session (no limits on cigarette or HT consumption) with the same study product used during the morning controlled use session.

On Days 3 and 4, puff topography will be performed during the last 2 hours of the 4-hour *ad libitum* product use session. The SPA-M topography device will collect data for 2 hours. The topography session will span a 2-hour period and the SPA-M topography device will be stopped and restarted with each new stick or cigarette during that time.

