12.4 Adverse Events

AE will be coded (to the preferred term) with Medical Dictionary for Regulatory Activities (MedDRA®) Version 24.1.

A study product use-emergent adverse event (PUEAE) is defined as an AE that is starting or worsening at the time of or after study product administration. Each PUEAE will be attributed to a product based on the onset date and time of the AE. AEs occurring prior to the first product use episode on Day 1 but after the product trial has started on Day -1 will be attributed to the product trial.

All events captured in the database will be listed in by-subject data listings. However, only PUEAEs will be summarised.

Frequencies of subjects with PUEAEs, regardless of relationship to study product will be summarised by study product and sorted by system organ class and preferred term. The number of PUEAEs will be tabulated in a similar manner. Tables which summarize the number of PUEAEs and number of subjects with PUEAEs by severity and relationship to study product will also be included.

Subjects only enrolled in the product trial and dropped prior to randomisation will be summarised separately.

Serious adverse events (SAEs), if present, will also be listed. Applicable narratives will be included in the CSR.

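### No scheduled AE question closes the 4-hour ad libitum session, so on Days 1–3 the next one comes about 14–17 hours later, after permitted own-brand smoking

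*Protocol*

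**What the plan says.** **AE inquiry.** Protocol 6.4.5.1 asks subjects to report events themselves and adds a staff question: "a specific inquiry regarding AEs will be conducted prior to each product use and at discharge" (or at early withdrawal). The question is open-ended.

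**The study day.** In the morning subjects "completely use a single unit of the assigned study product, with puffs taken at 30-second intervals and puffs 3 seconds in duration" (Protocol 6.3). Then, "following the 4-hour PK blood collection, subjects will start a 4-hour" ad libitum session (Protocol 3.1). Protocol 6.3 describes it as a "product use session (no limits on cigarette or HT consumption) with the same study product used during the morning controlled use session". It finishes "approximately 8 hours after the start of the morning controlled product use" (Protocol 6.4.3). Own cigarettes are then permitted until the overnight abstinence of at least 12 hours begins (Protocol 4.3.5).

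**Attribution.** SAP 12.4 states: "Each PUEAE will be attributed to a product based on the onset date and time of the AE". Events between the Day -1 product trial and the first Day 1 use have their own category. Evening own-brand smoking has none, and the AE table shells offer only Product Trial, A, B, C, D and Overall.

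**The concern.** Protocol objective 2.1, secondary 4, is the tolerability and safety of each product. The ad libitum session is the only period in which a product is used without limit, yet no scheduled question follows it closely on three of the four days.

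No other structured safety measure fills the gap:

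- The Product Evaluation Scale asks about dizziness, nausea and side effects, but it is completed just after the 240-minute blood draw (Protocol 6.4.2), before the session starts.
- Vital signs on Days 1–4 are taken before morning use (Protocol 6.4.4.4).
- Laboratory tests and ECGs are repeated only at end of study or early termination (SAP 12.5, 12.7).

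AE reports are therefore the main safety evidence that can be split by product. Mild, short-lived symptoms are the ones most easily forgotten or mis-timed when the question comes the next morning. Because the SAP assigns events by onset time, a poorly placed onset can become a poorly placed product.

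**Working it through.** The documents give no figure for this lag, so there is nothing to reproduce. The check is a timeline plus a count from the sequences.

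**Inputs**

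- Ad libitum start: 4 h after the start of morning use (Protocol 3.1).
- Ad libitum length: 4 h (Protocol 3.1).
- Abstinence before the next morning's use: at least 12 h (Protocol 4.3.5).
- Interval between morning sessions: about 24 h. This is an assumption. Protocol 6.4.3 fixes only the daily start of the unlimited session: "product use session on Days 1 through 4 will start at approximately the same time each day, with lunch served at the start". Range used: 23–25 h.
- Lead time of the morning inquiry: 0–2 h before use. This is also an assumption, borrowed from the vital-signs window in Protocol 6.4.4.4.
- Sequences: ABCD, BDAC, CADB, DCBA, with 24 subjects (Protocol 4.5, 3.1). Six per sequence is assumed.

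**Scheduled inquiries on Days 1–3**, reading a product use as a study-product session: 0 h (before the morning unit), 4 h (before ad libitum use), then about 24 h.

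**Lag from end of session to next question** = cycle − end of session

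- End of session = 4 + 4 = 8 h, i.e. 480 minutes.
- Base case: 24 − 8 = 16 h.
- Cycle of 23 to 25 h: 23 − 8 = 15 h to 25 − 8 = 17 h.
- Inquiry up to 2 h before use on a 24 h cycle: 24 − 2 − 8 = 14 h.
- Varying one input at a time gives 14–17 h. Setting both to their short end gives 23 − 2 − 8 = 13 h.

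**Own-brand window before that question** = (cycle − abstinence) − end of session = (24 − 12) − 8 = 4 h at most, because the abstinence is a minimum.

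**Day 4:** the discharge inquiry falls on the same day, so the overnight lag does not arise.

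**Product-days**

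- All products: 24 × 4 = 96, of which 24 × 3 = 72 fall on Days 1–3.
- Each product appears once in each day position across the four sequences, so with six subjects per sequence each product falls on each day 6 times.
- Heated-tobacco product-days: 3 products × 24 = 72. On Day 4: 3 × 6 = 18. On Days 1–3: 72 − 18 = 54, or 75%.
- Own-brand (Product D) days on Days 1–3: 72 − 54 = 18. There the evening product is the study product, so there is no second product to confuse it with.

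**The case against.** **The phrase may already cover it.** The protocol asks before each product use, without saying that a use means a session, and elsewhere it does say session when it means one. Read literally, every stick is a use. Alternatively, since own brand is Product D and SAP section 6 counts it as a study product, evening smoking would trigger a question at about 8 h and close the gap. What stands is that the phrase is undefined and the protocol should say which meaning applies. But an interview before every stick in an unlimited session is strained, and so is treating evening own-brand smoking, which falls outside the assigned sessions, as study-product use.

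**The flow chart may show continuous review.** In the extracted Table 1, the AE-review row has a mark at Screening and one other whose column is lost; it may be a bar across the stay. I therefore do not rely on that row. Even a bar would not set a time for the question.

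**Other capture continues.** Subjects are confined and told to report events, staff observations count, safety is monitored through the day, and onset date and time go on the CRF for every AE. This stands. A reader might infer that events from the session go unrecorded, or that all onset times are recalled a day late; the documents do not support that. The protocol nonetheless adds the staff question to self-report, so it does not treat self-report as sufficient.

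**Balance.** A reader might infer that the delay favours one product. It does not: with equal allocation and no dropout, every product meets it equally often.

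**Exposure.** A reader might call this the heaviest exposure of the day. That is an inference from unlimited use against one morning unit; the documents give no amounts.

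**Conclusion.** On the ordinary reading of Protocol 6.4.5.1, the point holds as a modest gap in safety ascertainment. On Days 1–3 the next scheduled AE question comes about 14–17 h after the session ends, with up to about 4 h of own-brand smoking in between; on Day 4 it comes at discharge.

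The consequences are limited to three:

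- poorer capture and onset timing of mild, brief events, on up to 72 of 96 product-days;
- uneven ascertainment between Days 1–3 and Day 4;
- less certain attribution on about 54 of 72 heated-tobacco product-days. It would be an overstatement to extend this to all 72 product-days on Days 1–3, since 18 of those are own-brand days.

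These figures assume a cycle of about 24 h, six subjects per sequence and no dropout. AE reporting is descriptive, and the primary PK comparison is untouched.

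**What to change.** 1. **Protocol 6.4.5.1 and Table 1:** add one open-ended AE inquiry at about 480 minutes on Days 1–4, after the ad libitum session and before own cigarettes are released, with onset times recorded then. If the sponsor believes an inquiry already falls there, define what counts as a product use so that this is explicit.
2. **SAP 12.4:** flag, or tabulate separately, AEs with onset after own-brand smoking resumes on heated-tobacco days. The recorded stop time of the session is a workable cut. Without this step, evening events would still have no category of their own, however well they are timed.

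The new question brings the lag on Days 1–3 from about 16 h to about 0 h.

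**Cost:** a sentence in 6.4.5.1, an entry in Table 1, a sentence and a footnote or column in the SAP, and one question per subject per day (24 × 4 = 96 in all). Staff already document each session's stop time (Protocol 5.2), so no extra contact is needed. The downside is that slightly more mild AEs will be recorded.
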